8.7.4 Vital Signs

Descriptive statistics for vital signs including blood pressures, respiration rate, and heart rate and changes from CL302 baseline values at each scheduled visit and at the end of study will be presented. All results of vital signs will be listed.

8.7.5 Physical and Neurological Exams

A complete physical examination including neurological exam is performed at CL302 baseline. At post-baseline visit, a subset of physical examination (brief exam including

general appearance, cardiovascular exam, and respiratory exam) is conducted. The number and percentage of abnormal findings will be summarized for the complete physical exam. The number and percentage of deficit findings will be summarized for the neurological exam. The number and percentage of abnormal findings for the brief exam will be summarized for post-baseline visits in a similar fashion.

8.7.6 Interval History

The Interval history in CL302 will be summarized for number and percentage of patients who reported changes at each visit from the last visit.

8.7.7 Suicidal Ideation

The Columbia Suicide Severity Rating Scale (C-SSRS) is a standardized rating instrument used to assess the suicidal ideation and behavior in an at-risk population and will be administered at each visit. Any 'Yes' response from C-SSRS will be listed.

8.7.8 Pregnancy Test

Pregnancy test will be conducted at the scheduled study visit and the results will be provided in a listing.

10 APPENDICES

10.1 Summary of Efficacy Endpoints and Analyses

Test / Instrument	Endpoint	Type of analysis	Time points for Assessment	Statistical approach at week 96/ET analysis
Subjects enrolling from UX001-202 and UX001-301				
Physical therapy – Hand-held Dynamometry (HHD)	The changes from baseline in Upper Extremity Composite (UEC) Score based on bilateral strength recorded in the following muscle groups: gross grip, shoulder abductors, elbow flexors, and elbow extensors	Primary analysis	Weeks 8, 16, 24, 48, 72, and 96	GEE Model
GNEM Functional Activities Scale (GNEM-FAS)	Changes from baseline on Upper Extremity Domain score	Secondary efficacy analysis	Weeks 8, 16, 24, 48, 72, and 96	GEE Model
	Changes on Mobility Domain score			
Physical therapy – Hand-held Dynamometry (HHD)	Changes from baseline in lower extremity composite score (LEC) based on bilateral strength recorded in the following muscle groups: knee flexors, hip flexors, hip extensors, hip abductors and hip adductors.	Secondary efficacy analysis	Weeks 8, 16, 24, 48, 72, and 96	GEE Model
	Changes from baseline in total force and percent predicted total force in the Knee Extensors.			
Sit to Stand	Change from baseline in the number of stands in the Sit-to-Stand test	Secondary efficacy analysis	Weeks 8, 16, 24, 48, 72, and 96	GEE Model
Weighed Arm Lift Test	Changes from baseline in the number of lifts in 30 second weighted arm lift tests	Secondary efficacy analysis	Weeks 8, 16, 24, 48, 72, and 96	GEE Model
6-Minute Walk Test	Changes from baseline in meters walked in 6MWT and percent predicted	Secondary efficacy analysis	Weeks 8, 16, 24, 48, 72, and 96	GEE Model

Test / Instrument	Endpoint	Type of analysis	Time points for Assessment	Statistical approach at week 96/ET analysis
Physical therapy – Hand-held Dynamometry (HHD)	Changes from baseline in UEC and LEC percent predicted based on reference equations adjusting for age, gender, height, and weight.	Tertiary efficacy analysis	Weeks 8, 16, 24, 48, 72, and 96	Summary statistics
	Changes from baseline in bilateral total force and percent predicted total force for each individual muscle group included in the UEC and LEC.			Summary statistics
GNEM Functional Activities Scale (GNEM-FAS)	Changes from baseline on the total score on the GNEM-FAS	Tertiary efficacy analysis	Weeks 8, 16, 24, 48, 72, and 96	Summary statistics
	Changes from baseline on the Self-Care Domain Score on the GNEM-FAS			Summary statistics
Individual Neuromuscular Quality of Life Questionnaire (INQoL) (Not including CL202 subjects)	Changes from baseline on the total score on a 45-item self-report questionnaire on the impact of key muscle disease symptoms on the ability to perform basic activities of daily living, functional independence, relationships and overall well-being	Tertiary efficacy analysis	Weeks 8, 16, 24, 48, 72, and 96	Summary statistics
Creatine Kinase (CK)	Changes from baseline in CK levels in serum to assess the degree of reduction of CK levels observed as a surrogate for muscle injury	Tertiary efficacy analysis	Weeks 8, 16, 24, 48, 72, and 96	Summary statistics

Subjects enrolling from UX001-203

GNEM Functional Activities Scale (GNEM-FAS) Expanded Version	Changes from baseline in the total scores	Primary efficacy analysis	Weeks 24, 48, 72, and 96	GEE Model
	Changes from baseline in the mobility domain			
	Changes from baseline in the upper extremity domain			
	Changes from baseline in the self-care domain			

Test / Instrument	Endpoint	Type of analysis	Time points for Assessment	Statistical approach at week 96/ET analysis
Physical therapy – Hand-held Dynamometry (HHD)	Changes from baseline in upper extremity muscle strength and percent predicted in the following muscle groups: grip, key pinch, shoulder abductors and wrist extensors	Primary efficacy analysis	Weeks 24, 48, 72, and 96	GEE Model
	Changes from baseline in lower extremity muscle strength and percent predicted in the knee extensors			
Short Form Health Survey – 36 (SF-36v2)	Changes from baseline in 8 subscales and summary scores (PCS and MCS) in SF-36v2	Exploratory efficacy analysis	Weeks 24, 48, 72, and 96	Summary statistics
Biomarker	Changes from baseline in serum biomarkers: creatine kinase (CK), serum aceneuramic acid	Exploratory efficacy analysis	Weeks 24, 48, 72, and 96	Summary statistics

10.2 Missing Observation in Hand Held Dynamometry and GNEM-FAS

Imputation rules outlined in this section for dynamometry are defined below and are based on the distinct pattern of muscle weakness associated with GNE Myopathy and the features of the dynamometers used in this study. The most common cause of missing data is muscle weakness severe enough to prevent the subject from registering the minimum amount of force against the dynamometer required to obtain a measurement during a maximum voluntary isometric contraction maneuver. In those cases, the value is imputed to 0, and preserves the ability to calculate the UEC and LEC scores. There are some scenarios in which non-random missing HHD data values result in missing UEC and LEC values. When strength in a particular muscle group exceeds the resistance that can be applied by the administrator, a reliable value cannot be obtained from the dynamometer. This is a recognized limitation of a hand-held device (Visser et al. 2003). In GNE Myopathy, the only muscle group at risk for this scenario is the knee extensors, due to the relative sparing of the quadriceps. All other non-random missing HHD data are related to the clinical condition of the subject at the time of the testing where a test may not be administered due to pain, injury, contracture or another extenuating circumstance that could cause discomfort to the subject. The proposed plan for the handling of this data is intended to provide the most accurate estimate of muscle strength and physical function possible based on knowledge of the disease and the outcome measures obtained during the conduct of previous studies.

Missing observations in HHD for individual muscle group will be imputed based on reason for missing and if the muscle strength measurement is missing on both sides or one side. The table below provides a summary of the imputation rule followed by detailed descriptions.

Instrument	Missing Reason	Imputation
HHD missing BOTH sides	Too Weak	0
	Too Strong	NA , UE/LE composite not computed
	Pain	NA , UE/LE composite not computed
	Injury	NA , UE/LE composite not computed
	Contracture	NA , UE/LE composite not computed
	Other	NA , UE/LE composite not computed
HHD missing ONE side	Too Weak	0
	All other reasons	The value from the other side that was measured

Missing Reason = Weakness

A value of 0 should be imputed for a W.

- If both sides are W, a value of 0 is assigned to each side and the muscle group IS counted as part of the UE or LE composite.
- If one side is W, a value of 0 is assigned to that side and the 0 is averaged with the value from the other side. The muscle group IS counted as part of the UE or LE composite.

Missing Reason = Contracture

A value of 0 should NOT be imputed for a C. A C is missing data because the test was not performed due to the contracture.

- If both sides are C (which would be rare), then the data for this muscle group is missing and the UE or LE composite will be set to missing.
- If one side is C, then the data is missing from this side and the value from the other side should be used to reflect the total strength for this muscle group. The muscle group IS counted as part of the UE or LE composite.

Missing Reason = Pain

A value of 0 should NOT be imputed for a P. A P is missing data because the test was not performed due to pain.

- If both sides are P, then the data for this muscle group is missing and the UE or LE composite will be set to missing.
- If one side is P, then the data is missing from this side and the value from the other side should be used to reflect the total strength for this muscle group. The muscle group IS counted as part of the UE or LE composite.

Missing Reason = Injury

A value of 0 should NOT be imputed for an I. An I is missing data because the test was not performed due to pain.

- If both sides are I, then the data for this muscle group is missing and the UE or LE composite will be set to missing.
- If one side is I, then the data is missing from this side and the value from the other side should be used to reflect the total strength for this muscle group. The muscle group IS counted as part of the UE or LE composite.

Missing Reason = Too Strong

An S indicates that the test was attempted but that the subject overpowered the administrator and a valid value could not be obtained.

- If both sides are S, then the data for this muscle group is missing and the UE or LE composite will be set to missing.
- If one side is S, then the data is missing from this side and the value from the other side should be used to reflect the total strength for this muscle group. The muscle group IS counted as part of the UE or LE composite.

Missing Reason = OTHER

No value should be imputed if there is an O.

- If both sides are O, then the data for this muscle group is missing and the UE or LE composite will be set to missing.
- If one side is O, then the data is missing from this side and the value from the other side should be used to reflect the total strength for this muscle group. The muscle group IS counted as part of the UE or LE composite.

When an individual question is missing in GNEM-FAS. The average score is calculated for the domain and then multiplied by the number of questions in the domain:

Mobility Subscale Score = $10 \times \text{Sum(Available Items)} / \text{Number of Available Items}$

Upper Extremity Subscale Score = $8 \times \text{Sum(Available Items)} / \text{Number of Available Items}$

Self-Care Subscale Score = $7 \times \text{Sum(Available Items)} / \text{Number of Available Items}$

If a domain has more than 50% (inclusive) items missing (≥ 5 for Mobility, ≥ 4 for Upper Extremity, ≥ 3 for Self-Care), the domain score will not be calculated. The Total FAS core will only be calculated if all three domain scores are available.

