#### **7.5.2.2 GNEM Functional Activities Scale**

**For UX001-CL202 and UX001-CL301 Subjects:** The GNEM-FAS (also referred to as HIBM-FAS in some studies) is a disease-specific measure developed to assess the functional impact of changes in muscle strength. The scale consists of 3 domains: upper extremity, mobility, and self-care; scores for each domain and a total score will be obtained. The scale has been developed specifically for patients with GNEM based on feedback received from affected individuals on the impact of the disease on their function. Items in the scale assess the subject's ability to independently perform various activities of living that involve self-care, mobility and use of the upper and lower extremities. The scale will be administered in an interview format by a trained clinician (preferably a licensed physical therapist) and scored after the testing. The physical therapists' role is a combination of observing subjects conducting activities and asking subjects questions to assess performance of these activities.

**For UX001-CL203 Subjects:** The original GNEM-FAS was developed as a clinician-reported outcome measure (ClinRO) for ambulatory GNEM patients but has since been modified to a self-report PRO format with items added to accommodate weaker

patients. This modified version is referred to as the GNEM-FAS Expanded Version and will be used for subjects rolling over from the UX001-CL203 study.

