- Change from baseline in the total score from a 45-item self-report questionnaire (INQoL) on the impact of key muscle disease symptoms on the ability to perform basic activities of daily living, functional independence, relationships and overall well-being;
- Changes from baseline in CK levels in serum to assess the degree of reduction of CK levels observed as a surrogate for muscle injury.

For subjects enrolling from UX001-CL203:

Primary Clinical Efficacy Endpoints:

- Changes from baseline in the mobility domain of GNEM-FAS Expanded Version;
- Changes from baseline in the upper extremity domain of GNEM-FAS Expanded Version;
- Changes from baseline in the self-care domain of GNEM-FAS Expanded Version;
- Changes from baseline in the total scores of GNEM-FAS Expanded Version;
- Changes from baseline in upper extremity muscle strength and percent predicted in the following muscle groups: grip, key pinch, shoulder abductors and wrist extensors as measured by HHD
- Changes from baseline in lower extremity muscle strength and percent predicted in the knee extensors as measured by HHD

Exploratory endpoints:

- Changes from baseline in 8 subscales and summary scores (PCS and MCS) in health-related quality of life as assessed by using Short Form Health Survey – 36 (SF-36v2);
- Changes from baseline in creatine kinase (CK) and serum aceneuramic acid.

Assessments, upon which efficacy endpoints are based on, are shown in [Table 4.2.1](#). Detailed information on efficacy endpoints and visit schedules by study can be found in [Appendix 10.1](#).

Table 4.2.1: Efficacy Assessments Performed by Parent Study

	CL202 and CL301	CL203
Assessment	Week 0, 8, 16, 24, 48, 72, 96	Week 0, 24, 48, 72, 96
Functional	HHD* 6MWT Sit-to-Stand Test Weighted Arm Lift Test GNEM FAS	HHD^ GNEM FAS expanded version
QoL Questionnaire	INQoL	SF-36 short form
Biomarker	CK Free serum SA Urine ManNAc	

* Measured by HHD, the Upper Extremity Composite (UEC) Score is based on gross grip, shoulder abductors, elbow flexors, and elbow extensors. The Lower Extremity Composite (LEC) Score is based on knee flexors, hip flexors, hip extensors, hip abductors, and hip adductors.

^ Measured by HHD, UEC is not defined in this study for analysis, since different muscle groups from the other two studies are measured. Lower extremity muscle strength of knee extensors is included.

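### The GNEM-FAS missing-item rule fixes one set of item counts for two versions of the scale, so incomplete forms can be scored on a different scale from complete ones

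*SAP*

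**What the plan says.** SAP 7.2.2 sends the reader to Appendix 10.2 for missing GNEM-FAS questions and does not mention versions. The rule there has a trigger, "When an individual question is missing in GNEM-FAS", and a general statement: "The average score is calculated for the domain and then multiplied by the number of questions in the domain". Three formulas follow. They multiply the mean of the available items by 10 for Mobility, 8 for Upper Extremity and 7 for Self-Care. A domain is not scored when half or more of its items are missing, and the appendix turns that into counts: "≥ 5 for Mobility, ≥ 4 for Upper Extremity, ≥ 3 for Self-Care". The total is calculated only if all three domain scores exist.

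Protocol 7.5.2.2 describes two instruments. CL202 and CL301 subjects receive the clinician-administered GNEM-FAS. CL203 subjects receive a version that "has since been modified to a self-report PRO format with items added to accommodate weaker" patients, called the Expanded Version. The SAP schedule of events (Appendix 10.5, footnote k) confirms this.

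For CL203, SAP 4.2 lists the three Expanded Version domain scores as primary clinical efficacy endpoints, together with "Changes from baseline in the total scores of GNEM-FAS Expanded Version". Appendix 10.1 assigns them to the GEE model.

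**The concern.** If one version contains items that the other lacks, at least one domain differs in length between them, and a single set of multipliers and cut-offs cannot serve both. The Protocol mentions additions only and no removals.

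The trigger makes this more than a labelling matter. The proration applies when an item is missing. On a literal reading, a complete Expanded form is summed over its full length, while a form with one gap is scaled to 10, 8 or 7 items. Two visits of the same subject then sit on different scales, and their difference contains a shift unrelated to function.

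A gap at baseline affects every later change score for that subject in that domain. It also enters the model as the baseline covariate (SAP 8.6). CL203 is analysed against both the parent-study and the current-study baseline (SAP Table 8.1.1), so either can be affected. Because the total needs all three domains, an error in one domain carries into it. The cohort is small: Protocol 7.6.1 expects 30 subjects from CL203.

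**Working it through.** **Inputs from the documents.** Multipliers k = 10, 8, 7 and cut-offs 5, 4, 3 (SAP Appendix 10.2); CL203 N = 30 (Protocol 7.6.1).

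**Not in the documents.** The Expanded Version's item counts, the domains that gained items, whether 10/8/7 are the original counts, and the direction of scoring. I take 10/8/7 as the original counts and assume a = 1 to 5 items added to a domain, so that its true length is K = k + a.

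**Step 1: the plan's own cut-offs.** Half or more missing means at least k/2 items, rounded up.
- Mobility: 10/2 = 5, as stated.
- Upper Extremity: 8/2 = 4, as stated.
- Self-Care: 7/2 = 3.5, so 4. The SAP states 3, and 3/7 = 42.9%, which is under half.

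Two of the three reproduce. The Self-Care cut-off contradicts its own rule even for a seven-item domain.

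**Step 2: the rule on a form of length k.** Hold every item at the same level m, with one item missing. Prorated score = k × (k − 1)m/(k − 1) = km, the complete score. There is no artefact when the constant matches the form.

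**Step 3: the same formula on a form of length K.** Complete score = Km. Literal score with a gap = km. Ratio = k/K.
- Gap at a post-baseline visit only: apparent change = k/K − 1.
- Gap at baseline only: apparent change = K/k − 1, relative to the shrunken baseline. The shift in points is the same size with the opposite sign.

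| Domain | k | K (a = 1 to 5) | Post-baseline gap | Baseline gap |
|---|---|---|---|---|
| Mobility | 10 | 11 to 15 | −9.1% to −33.3% | +10.0% to +50.0% |
| Upper Extremity | 8 | 9 to 13 | −11.1% to −38.5% | +12.5% to +62.5% |
| Self-Care | 7 | 8 to 12 | −12.5% to −41.7% | +14.3% to +71.4% |

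With a = 0 the shift is 0%. If the multiplier is K, as the general sentence implies, the shift is 0% for any K.

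**Step 4: gaps at both visits, or the formula applied to every form.** Both scores are scaled by k/K. No change appears where none occurred, but a real change is shrunk by k/K.

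**Step 5: group mean.** Shift = (share affected) × (k/K − 1). For Mobility with K = 12 (assumed), k/K − 1 = −16.7%.
- 1 of 30 affected at a visit: −0.56% of the domain score.
- 10% affected (assumed): −1.67%.
- 20% affected (assumed): −3.33%.

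**Step 6: cut-offs on a longer form.** With K = 12, five missing items are 5/12 = 41.7%. The half-or-more rule would require 6.

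**Step 7: the reverse case.** If 10/8/7 are the Expanded counts, the original form is mis-scored instead. A nine-item original Mobility domain (assumed) with a gap would be inflated by 10/9 − 1 = +11.1%. That would affect the CL202/CL301 secondary endpoints (Mobility and Upper Extremity domains) and tertiary endpoints (Self-Care and total).

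**The case against.** The strongest reply is that the general sentence in Appendix 10.2 is already right. It refers to the number of questions in the domain, which is version-neutral, and the half-missing rule is also stated generally before the counts in brackets. A programmer who follows the words produces no artefact, and one who met a form longer than the formula allows would probably ask. This stands as far as it goes. However, the formulas and counts are the operative text, and no Expanded Version item count appears in either document. The words therefore cannot be carried out from the plan alone.

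A second reply is that the SAP's endpoint lists separate GNEM-FAS from its Expanded Version, so Appendix 10.2 may cover only the original. This is arguable, but usage is not uniform: the CL203 row of the schedule of events says GNEM-FAS with a footnote. On that reading there is no rescaling. Instead, the CL203 primary efficacy scores have no missing-item rule, although SAP 7.2 anticipates missing item scores and SAP 8.1 rules out imputation unless stated.

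A reader might also infer that the rule creates a false decline in all the CL203 primary efficacy scores. The documents do not support that. They do not say which domains gained items or whether a higher score means better function, and a baseline gap reverses the sign. Nor do they give a missing-item rate, so the per-subject percentages do not measure bias in the analysis.

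**Conclusion.** The inconsistency is real. The fixed multipliers and cut-offs cannot be right for both versions, and applied literally they put incomplete and complete forms of at least one version on different scales.

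The size is conditional. If 10/8/7 are the original counts and a domain gained 1 to 5 items, a post-baseline gap shifts an affected subject's score by −9% to −33% (Mobility), −11% to −38% (Upper Extremity) or −12.5% to −42% (Self-Care), with the opposite sign for a baseline gap. These figures hold item level constant. A domain with no added items is unaffected. The group effect is small if gaps are rare: about 0.6% of the Mobility score per affected subject, with N = 30 and 12 items assumed.

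This does not touch the study's primary endpoint, which is safety (Protocol 7.2; SAP 4.1.1). The CL203 scores are primary efficacy endpoints of one cohort in a single-arm extension. The point merits correction because the error is avoidable and the plan's explicit formulas would produce it.

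**What to change.** In SAP Appendix 10.2:
- List the number of items per domain for the original GNEM-FAS and for the Expanded Version.
- Define the domain score as that number, for the version administered, times the mean of the answered items.
- Replace the fixed cut-offs with version-specific ones derived from the stated half-or-more rule. For a seven-item Self-Care domain this gives 4, not 3; if 3 is intended, the rule in words should say so.
- State that the rule covers both versions.

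The cost is a few lines of SAP text and version-specific constants in the scoring program. No new data are needed, and the artefact disappears for any item count.

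### SAP 10.2 sets the GNEM-FAS Self-Care cut-off at 3 of 7 missing items (42.9%), which does not meet the 50% rule it is meant to implement

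*SAP*

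**What the plan says.** SAP Appendix 10.2 prorates a GNEM-FAS domain that has missing items: "The average score is calculated for the domain and then multiplied by the number of questions in the domain". The multipliers are 10 for Mobility, 8 for Upper Extremity and 7 for Self-Care, so by the SAP's own description these are the item counts.

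The limit on proration follows, as a percentage with the counts that go with it: "If a domain has more than 50% (inclusive) items missing (≥ 5 for Mobility, ≥ 4 for Upper Extremity, ≥ 3 for Self-Care". When that limit is reached, the domain is not scored.

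The Total depends on all three domains: the Total FAS "core will only be calculated if all three domain scores are available".

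SAP Section 4.2 makes the Self-Care and Total scores tertiary endpoints for subjects from CL202 and CL301. For subjects from CL203 it lists the Self-Care and Total scores of the GNEM-FAS Expanded Version among the primary clinical efficacy endpoints. Protocol Section 7.5.2.2 describes the Expanded Version as a self-report form to which items were added for weaker patients.

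**The concern.** One sentence gives the same rule twice, as a percentage and as a count, and for Self-Care the two disagree. A programmer who codes the percentage keeps a form with 4 of 7 Self-Care items answered. One who codes the listed count drops it. Each could claim to have followed the SAP, and their datasets would differ.

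Nothing else in the documents settles the matter. Protocol Section 7.6 leaves the handling of missing data to the SAP, SAP Section 1 gives the SAP precedence on analysis methods, and neither document explains a stricter limit for Self-Care. The study is open-label, so the choice should be fixed in writing and not made with scores in view.

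At stake are Self-Care scores on forms with exactly 3 items missing, and Totals that could otherwise have been computed. SAP Section 8.1 does not impute missing data unless stated otherwise, so those visits would drop out of both summaries.

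**Working it through.** **Inputs, all from SAP 10.2 unless noted**
- Items per domain (k): 10, 8, 7, from the scoring formulas.
- Rule: no score when the missing share is 50% or more.
- Listed cut-offs: 5, 4, 3.
- Item-missingness rate: not given in either document.

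**Step 1. Reproduce the cut-offs.** On the inclusive reading, the cut-off is the smallest whole number m with m/k ≥ 0.5, that is ceil(k/2). The wording mixes a strict and an inclusive phrase, so the strict reading, floor(k/2) + 1, is shown too.

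| Domain | k | Listed | Listed as % | Inclusive | Strict |
|---|---|---|---|---|---|
| Mobility | 10 | 5 | 50.0% | 5 | 6 |
| Upper Extremity | 8 | 4 | 50.0% | 4 | 5 |
| Self-Care | 7 | 3 | 42.9% | 4 | 4 |

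Mobility and Upper Extremity reproduce under the inclusive reading. Self-Care reproduces under neither: both give 4 (4/7 = 57.1%). A 3 arises only if 3.5 is rounded down, or if the domain has six items (3/6 = 50%), which conflicts with the multiplier of 7.

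**Step 2. Which forms are affected.** With 0 to 2 items missing, both versions score the domain. With 4 to 7 missing, neither does. Only forms with exactly 3 of 7 missing are treated differently.

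**Step 3. How many, for illustration only.** Assume each item is missing independently with probability p. Then P(exactly 3 of 7) = 35 × p³ × (1 − p)⁴. For p = 0.10 this is 35 × 0.001 × 0.6561 = 0.0230.

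The Total is lost if any domain is unscorable: 1 − (1 − a)(1 − m)(1 − u). Here a, m and u are the binomial probabilities of reaching the cut-off for Self-Care, Mobility (5 of 10) and Upper Extremity (4 of 8).

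| p | Exactly 3 of 7 missing | Total lost, cut-off 3 | Total lost, cut-off 4 |
|---|---|---|---|
| 2% | 0.03% | 0.03% | 0.002% |
| 5% | 0.36% | 0.42% | 0.06% |
| 10% | 2.3% | 3.2% | 0.9% |
| 20% | 11.5% | 22.2% | 11.8% |

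**Step 4. As a number of forms.** Protocol Section 7.6.1 expects 55 subjects from CL202 and 80 from CL301, and SAP Table 4.2.1 gives seven visits. With full attendance that is 135 × 7 = 945 forms. The expected number with exactly 3 of 7 missing is about 0.2 at 2%, 3.4 at 5%, 22 at 10% and 108 at 20%.

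**The case against.** The strongest case on the other side is that this matters little and that the right correction is not certain.

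- **Low tier.** For CL202 and CL301 both scores are tertiary, and SAP Appendix 10.1 assigns them summary statistics only (although Section 8.6 names GEE for all continuous efficacy endpoints). The UEC and the secondary Mobility and Upper Extremity domains are untouched, and the study's primary endpoint is safety. This stands.
- **Few forms.** For these subjects a trained clinician administers the scale by interview (Protocol 7.5.2.2), so a high item-missingness rate would be surprising. This also stands as a caution: the 20% row is an outer illustration, not a forecast.
- **Intent unknown.** The count of 3 is explicit and can be programmed, and someone may have wanted a stricter limit. The documents do not exclude that, but they do not say it, and a stricter limit would still contradict the percentage in the same sentence. The slip could also lie in the item count.

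Three stronger readings are tempting. A reader might infer that the error removes CL203 primary endpoint data, since Self-Care and Total are listed there. That is not shown: those subjects complete the Expanded Version, and 10.2 does not say that its 10, 8 and 7 apply to it. A reader might also infer that every Self-Care score dropped by the cut-off costs a Total. It does so only when the other two domains are scorable; at 20% missingness the added loss of Totals is 22.2% − 11.8% = 10.4%, against 11.5% for Self-Care. Finally, a reader might infer bias because the losses fall on less complete forms. That is true of any missing-item limit and does not by itself show bias.

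**Conclusion.** The contradiction is real and does not depend on how the 50% phrase is read. With seven items, the stated rule first withholds the score at 4 missing, not 3. As listed, forms with exactly 3 of 7 Self-Care items missing lose a score that the rule keeps, and some of them lose the Total as well.

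The established reach is the tertiary Self-Care and Total scores for subjects from CL202 and CL301. For CL203 the effect is undetermined. The size cannot be fixed from the documents; under independent missingness of 2% to 20% it runs from about 0.03% to 11.5% of forms, and it is well under 1% at 5% or below. That a cut-off of 4 is the right correction rests on two conditions: that the domain has seven items, and that the inclusive 50% rule is intended. The formula supports the first and the other two cut-offs support the second.

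**What to change.** In SAP 10.2:
1. Confirm against the instrument that Self-Care has seven items.
2. If so, change the Self-Care cut-off from 3 or more to 4 or more, so that all three domains follow the inclusive 50% rule. If the domain has six items, keep 3 and correct the multiplier of 7 instead; otherwise prorated Self-Care scores would be too high by a factor of 7/6.
3. Reword the percentage as 50% or more, to remove the mixed phrasing.
4. State whether the rule covers the Expanded Version used for CL203 subjects, and give its item counts and cut-offs.

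If a stricter Self-Care limit was intended, say so and give the reason. The cost is one digit in the SAP, one programming constant and a sentence or two on the Expanded Version. No data collection changes.
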